6 EFFICACY ASSESSMENTS

6.1 Specification of the efficacy parameters

Efficacy parameters are outlined as follows:

- MADRS evaluation
- CGI evaluation
- HAM-D-17 evaluation
- HAM-A evaluation
- DSSS evaluation

6.2 Methods and Timing for Assessing, Recording, and Analyzing of Efficacy Parameters.

The data obtained from eligible subjects before study drug administration in Visit 2 are set as baseline. After the beginning of treatment, the collection of data of efficacy parameters are performed at planned treatment schedule as section 5.2. CRC shall record these data in CRF in detail after each visit during the treatment period. In part I, efficacy assessments are conducted from screening stage to the last visit. In part II, data

comparison between group of 1 capsule TID, 2 capsules TID of PDC-1421 Capsule and placebo will be conducted in final report of this study to evaluate which group(s) of PDC-1421 Capsule are efficient. The rating scales are as follows:

- **MADRS (Montgomery- Å sbergDepression Rating Scale)**

The MADRS is a 10-item checklist including 1) depression [apparent]; 2) depression [reported]; 3) loss of interest; 4) suicidal ideation; 5) tension; 6) reduced appetite; 7) insomnia; 8) difficulty in activities; 9) concentration; and 10) pessimism. Each Item is rated on a scale of 0-6, with anchors at 2-point intervals; higher scores indicating more severity (i.e., ranging from 0 [no sadness] to 6 [extremely despondent]). Percentage of partial responders (defined as a participant with a 25-50%decrease from baseline in total score) and responders (defined as a participant with $\geq 50\%$ decrease from baseline in total score.). The following are as an interpretation of scores:

Recovered, 7

Mild, 15

Moderate, 25

Severe, 31

Very severe, 44

- **CGI (Clinical Global Impression)**

The CGI actually comprises two companion one-item measures evaluating the following: (a) CGI-Severity (CGI-S) which rates illness severity of psychopathology from 1 to 7 and (b) CGI-Improvement (CGI-I) which rates change from the initiation (baseline) of treatment.

- **HAM-D-17 (Hamilton Rating Scale for Depression)**

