### 6.4.1 Primary Efficacy Endpoint

In part II study, the primary endpoint is the net change of the MADRS total score at the 6th week after treatment (Mean MADRS total score at week 6 – Mean MADRS total score at baseline [Visit 2]).

Kruskal-Wallis test will be implemented to test the group difference.

The primary hypothesis will be:

$$\begin{aligned}
 H_0: & \text{The mean ranks of the groups are the same} \\
 H_a: & \text{The mean ranks of the groups are not the same}
 \end{aligned}$$

One a significant treatment effect is found, Wilcoxon rank sum test with Holm procedure will then be performed for comparisons between two treatment groups and the placebo group. The treatment group will be declared superior if null hypothesis is rejected and  $\mu_{t1}$  and/or  $\mu_{t2}$  is greater than  $\mu_p$ .

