**CONFIDENTIAL**

Project No. BLI-1005-002

Statistical Analysis Plan for PDC-1421

“Final” Page 23 of 34

Protocol Version: 2.3

SAP Version: 20180626\_01

second batch are “HDP-045A-070119” for PDC-1421 and “HDP-045C-070119” for placebo. Subjects with baseline visit later than 2018/02/13, or those who were enrolled before 2018/02/13 and got drugs after 2018/03/15 will be classified into the subgroup of the second batch.

The responder and partial responder is defined by the net change in total score of MADRS (responders are defined as participants with a  $\geq 50\%$  decrease in total score from baseline; partial responders are defined as participants with at least 25% and no more than 50% decrease in total score from baseline). The percentage difference between treatment groups will be examined by Cochran-Mantel-Haenszel test.

The same definitions of partial responder will be used for HAM-D-17. The difference between the treatment will be compared with Cochran-Mantel-Haenszel test as well.

All statistical tests used will be two-tailed with  $\alpha = 0.05$ .

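### The rule that declares a dose superior on the primary endpoint points the wrong way: it asks for a larger week-6-minus-baseline MADRS change than placebo, when benefit is a smaller one

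*SAP*

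**What the plan says.** SAP section 6.4.1 gives the primary endpoint as a net change in MADRS total score, written as "Mean MADRS total score at week 6 – Mean MADRS total score at baseline". Protocol section 6.2 describes the MADRS items with "higher scores indicating more severity". SAP section 6.4.2 and Protocol section 3.3 both define response as a decrease from baseline.

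The test sequence in SAP 6.4.1 has no direction of its own. First, "Kruskal-Wallis test will be implemented to test the group difference", with the alternative stated as "The mean ranks of the groups are not the same". If that is significant, "Wilcoxon rank sum test with Holm procedure will then be performed for comparisons between two treatment groups and the placebo group". SAP section 5.3.3 makes the tests two-sided at 0.05.

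Direction enters only in the last sentence of 6.4.1: "The treatment group will be declared superior if null hypothesis is rejected and", followed by the condition that μt1 and/or μt2 be greater than μp. None of the three symbols is defined anywhere in the SAP.

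**The concern.** The subtraction makes improvement negative, while the superiority condition asks for the dose to be greater than placebo. On a scale where higher is worse, these conflict.

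This sentence is the only one that turns a significant primary test into a claim for a dose, and SAP section 6.1 rests the primary conclusion on this endpoint in the ITT population. Applied as written, it would deny the claim to an effective dose and could give it to a harmful one. If the analysts instead correct it silently, the direction of the primary claim is settled outside the pre-specified plan, possibly after the results are known.

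**Working it through.** **1. Sign of the endpoint.** Change = week 6 − baseline (SAP 6.4.1). Higher MADRS is worse (Protocol 6.2), so improvement means change < 0. A dose better than placebo has change(dose) < change(placebo).

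**2. Sign of the rule.** The rule requires μt > μp. The possible readings of μ are:

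| μ read as | A better dose has | Rule as written |
|---|---|---|
| mean change (week 6 − baseline) | smaller μ | wrong direction |
| mean rank of the change | smaller μ | wrong direction |
| mean week 6 score (similar baselines) | smaller μ | wrong direction |
| size of the reduction (baseline − week 6) | larger μ | right, but contradicts the formula in 6.4.1 |

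**3. Worked example of one dose-versus-placebo comparison.** The values are illustrative and not from the documents. Take 20 placebo changes equally spaced from −20 to 0 (mean −10), and 20 dose changes each 8 points lower (mean −18).
- The spacing is 20/19 = 1.053, so a shift of 8 is 7.6 steps. A dose value exceeds a placebo value only when it is at least 8 positions ahead: 12 + 11 + … + 1 = 78 of the 400 pairs.
- Mean rank, dose: 10.5 + 78/20 = 14.4. Mean rank, placebo: 10.5 + 322/20 = 26.6.
- Wilcoxon: z = (200 − 78 − 0.5)/√(400 × 41/12) = 121.5/36.97 = 3.29, two-sided p = 0.001.

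The dose is clearly better, and lower on both the mean and the mean-rank scale, so the greater-than condition refuses the claim.

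**4. Simulation of the full procedure.** From the documents: 60 subjects allocated 1:1:1, so 20 per arm; Kruskal-Wallis at 0.05; then two-sided Wilcoxon tests of each dose against placebo with Holm (smaller p against 0.025, the other against 0.05). The sample-size sections (Protocol 8.1, SAP 5.3.4) give no effect size, SD or power, so there is no planned figure to reproduce. Assumed: normal changes, placebo mean −10, SD 8 or 10, and the same true effect in both doses. There were 4,000 runs per row, with Monte Carlo standard error at most √(0.25/4000) = 0.008. μ is taken as the mean change. Probability that at least one dose is declared superior:

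| SD | True effect of both doses | As written (greater than) | Corrected (less than) |
|---|---|---|---|
| 8 | 3 points better | 0.0003 | 0.18 |
| 8 | 5 better | 0.000 | 0.46 |
| 8 | 8 better | 0.000 | 0.88 |
| 10 | 3 better | 0.0008 | 0.13 |
| 10 | 5 better | 0.000 | 0.29 |
| 10 | 8 better | 0.000 | 0.68 |
| 8 | none | 0.018 | 0.016 |
| 10 | none | 0.017 | 0.017 |
| 8 | 5 worse | 0.46 | 0.000 |
| 8 | 8 worse | 0.87 | 0.000 |
| 10 | 5 worse | 0.29 | 0.000 |
| 10 | 8 worse | 0.68 | 0.000 |

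A separate run with integer-rounded scores, SD 10, an effect of 9 points (0.9 SD) and 20,000 replicates gave 0.0% as written against 78.6% corrected for benefit, and 79.0% as written for harm.

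**The case against.** The strongest defence is that μ is undefined, and the author may have meant the size of the improvement, in which case the rule is right. That may well have been the intent. But the SAP does not say so, no section redefines change as baseline minus week 6, and that reading contradicts the subtraction printed in the same section. An undefined symbol in the primary decision rule needs correcting in any case.

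A second point is that the damage is confined to the declaration. The Kruskal-Wallis, Wilcoxon and Holm p-values do not change. SAP 6.4 still calls for means with confidence intervals, medians and line charts by treatment, and the responder analyses fix benefit as a decrease. A careful reader would see the true direction, so the conclusion reverses only if the sentence is applied literally. This stands as a limit on the practical effect. It does not make the rule correct.

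Third, the simulated percentages largely restate the sign, because reversing an inequality swaps near-zero with the power. That is fair: they depend on an SD and effects that the documents do not give, and the 0.9 SD case lies towards the favourable end. They show the range of consequences and are not needed to establish the error.

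Finally, means and mean ranks can differ in direction when data are skewed or tied. The simulations used normal data and do not test this. It is a minor further reason to define μ.

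**Conclusion.** The concern holds. With change defined as week 6 minus baseline, the superiority condition in SAP 6.4.1 has the wrong direction under every reading of μ that fits that definition, and no other text supplies the right one. The sign finding rests on the documents alone.

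Its size, under the assumptions above (20 per arm, normal changes, SD 8 to 10, equal effects in both doses): for doses 3 to 8 points better, a claim has probability at most 0.001 as written against 0.13 to 0.88 once corrected; for doses 5 or 8 points worse, it is 0.29 to 0.87 as written. Test statistics, p-values and estimates are untouched. Because this is the only directional rule for the primary endpoint, it must be fixed before it is applied.

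**What to change.** Amend two statements in SAP 6.4.1.

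- **Endpoint:** define the change as each subject's own week 6 MADRS total minus that subject's baseline (Visit 2) total. The present wording is a difference of two means, which cannot be ranked.
- **Decision rule:** replace the last sentence with wording such as: *After a significant Kruskal-Wallis test, a dose is declared superior to placebo if its Holm-adjusted two-sided Wilcoxon p-value is at most 0.05 and its mean rank of change in that comparison is lower than placebo's (a larger reduction). The rule is applied to each dose separately.*

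This removes the undefined μ symbols and the and/or, and judges direction on the scale that is tested. Defining change as baseline minus week 6 and keeping greater than would also work, provided every table and the secondary endpoints use the same sign. Only one convention should be adopted.

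The cost is a short amendment to an SAP already approved as final (version 01), ideally before unblinding. It needs no new data, no additional patients and no change to the tests.

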### 6.4.2 Secondary efficacy endpoints:

In the part II study, change from baseline in MADRS at week 2/4/7, along with net changes in HAM-D-17, HAM-A, DSSS, and CGI at week 2/4/6/7 are the secondary endpoints. Also, group differences in net changes of the MADRS, CGI, HAM-D-17, HAM-A, and DSSS at the 2nd, 4th, 6th, and 7th week are the secondary efficacy endpoints. For the results with regard to MADRS and HAM-D-17, the summary of all sites in Taiwan will also be provided to contrast with the one in America.

Descriptive statistics for original and changes from baseline will be display by part, center, visit and treatment. As for the group difference, it will be examined by Kruskal-Wallis test. A significant treatment effect will be claimed after the Wilcoxon rank sum test for post-hoc tests.

In addition to the treatment difference, the effect of different product batches (or batch number)- the first batch and the second batch, on MADRS will also be examined. Drugs with batch number of “HDP-045A-040327” and placebos with batch number of “HDP-045C-040327” are classified into the first batch of product. The batch numbers included in the

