### 5.2 Study Design

The screening phase is intended for diagnosing and assessing the patient for possible inclusion in the study and for providing an adequate washout period. The following study will be conducted in two parts. The targeted population of this study is 72 subjects who met the intent-to-treat (ITT) basis, in which 12 are assigned to part I, 60 are assigned to part II. Part I is an open-label study, multiple center and dose escalation evaluation in twelve patients. Six subjects each will be evaluated for any safety concerns at 1 or 2 capsules TID dose for 28 days, sequentially. Each of them will be assessed twice in the first week after administration of PDC-1421 Capsules and once a week in the following treatment. Part II is a randomized, double-blind, placebo-controlled, parallel-group study. 60 subjects will be randomly assigned on a 1:1:1 basis to one of the three treatment arms (1 PDC-1421 Capsule plus 1 placebo TID, 2 PDC-1421 Capsule TID, 2 placebo TID) for 6 weeks (42 days) and evaluated the safety and efficacy every two weeks during the treatment period. The performance of PDC-1421 Capsule on MDD subjects will provide us with valuable information for our next phase of the study.

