**5.3.3 Statistical Evaluation**

Simple descriptive statistics with 95% confidence interval will be performed with data collected in this study wherever applicable. Treatment effects are evaluated based on 2-sided test with a 0.05 significant level. All data shall be tabulated and presented in the study report. The descriptive statistics will be provided. The safety and efficacy data will be analyzed using the non-parametric method.

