### 6.1 Data Sets Analyzed

Two study populations are intention-to-treat (ITT) population and per-protocol (PP) populations which are defined in section 5.3.1.

The efficacy evaluations will be performed on both of the ITT and PP datasets while the safety evaluations will be performed on the ITT dataset. The primary conclusion will be made for the primary endpoint on the ITT population

Demographic and baseline (Visit 2) characteristics will be performed on the ITT population.

Sample size, mean, 95% confidence interval of mean, median, standard deviation, inter-quartile range, maximum and minimum will be summarized for continuous variables. For categorical variables, the frequency and percentage will be provided.

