### ***6.6.5 Multiple Comparisons / Multiplicity***

The Holm procedure will be carried out for the post-hoc test of the primary endpoint.

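### SAP 6.4.2 lets a significant effect be claimed on each of 19 secondary comparisons at 0.05 with no control across them, so the chance of a false secondary claim is well above 5%.

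*SAP*

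**What the plan says.** SAP 6.4.2 names the Part II secondary endpoints as "change from baseline in MADRS at week 2/4/7, along with net changes in HAM-D-17, HAM-A, DSSS, and CGI at week 2/4/6/7". On testing it says "As for the group difference, it will be examined by Kruskal-Wallis test", and then "A significant treatment effect will be claimed after the Wilcoxon rank sum test for post-hoc tests". The same section ends with "All statistical tests used will be two-tailed with" alpha of 0.05, which agrees with SAP 5.3.3: "Treatment effects are evaluated based on 2-sided test with a 0.05 significant level".

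Multiplicity is addressed once, in SAP 6.6.5: "The Holm procedure will be carried out for the post-hoc test of the primary endpoint". This matches SAP 6.4.1, where the primary endpoint has Kruskal-Wallis first and then Wilcoxon tests of each dose against placebo with Holm. SAP 6.4.2 names no such correction.

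Two passages limit the reach of the secondary results. SAP 6.1 says "The primary conclusion will be made for the primary endpoint on the ITT population". SAP 5.3.4 and Protocol 8.1 describe Part II as a small proof of concept. Neither document labels the secondary tests exploratory or nominal, ranks them, or makes them depend on a significant primary result.

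**The concern.** The difficulty is the combination of many tests, a full 0.05 for each, and a pre-specified statement that significance leads to a claim. The secondary rule is looser than the primary one: the two dose-against-placebo comparisons are Holm-adjusted at the primary endpoint and unadjusted everywhere else.

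A trial that misses its primary endpoint could therefore still report a significant treatment effect while following its own plan exactly. This matters because the primary objective (Protocol 2, SAP 5.1.1) is to find which doses work and how long to treat, and SAP 5.2 expects the results to inform the next phase. A chance finding on another scale or at another visit bears on both questions.

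**Working it through.** **Inputs from the documents**
- Secondary comparisons (SAP 6.4.2): MADRS 1 × 3 visits + 4 scales × 4 visits = 3 + 16 = 19. MADRS at week 6 is left out because it is the primary endpoint.
- Level: two-sided 0.05 per test (SAP 5.3.3 and 6.4.2).
- Sample size (SAP 5.2): "60 subjects will be randomly assigned on a 1:1:1 basis to one of the three treatment arms", so 60 / 3 = 20 per arm.
- Rule: Kruskal-Wallis at 0.05, then unadjusted Wilcoxon of each dose against placebo at 0.05.

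**Plan's own figure.** The plan states no error rate for the secondary family, so there is nothing to reproduce.

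**Simple benchmarks (Kruskal-Wallis step only)**
- Expected false rejections: 19 × 0.05 = 0.95, whatever the correlation.
- Chance of at least one if all 19 were independent: 1 − 0.95^19 = 0.623, or 62%.

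The tests are not independent, because related scales are measured repeatedly on the same patients. The 62% also counts Kruskal-Wallis rejections that no pairwise test would turn into a claim.

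**Simulation of the two-step rule.** No drug effect, 20 per arm, multivariate normal changes, 4,000 trials per setting, five scales at four visits. A claim means Kruskal-Wallis p < 0.05 and at least one dose-against-placebo Wilcoxon p < 0.05 on any of the 19. The correlations are assumptions; the documents give none.

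| Correlation between scales / visits | Any false claim | Any false claim, primary Kruskal-Wallis not significant | Any false claim favouring the drug |
|---|---|---|---|
| 0.3 / 0.3 | 50% | 47% | 28% |
| 0.5 / 0.5 | 43% | 40% | 23% |
| 0.7 / 0.6 | 35% | 31% | 18% |
| 0.8 / 0.7 | 28% | 24% | 15% |
| 0.9 / 0.9 | 15–18% | 12% | 8–9% |

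Repeat runs moved the first four rows by about two points at most. The last row varied more between runs, and about 17% is a fair summary of its any-claim figure.

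**Reading the table**
- Against the nominal 5%, any false claim is inflated 28 / 5 = 5.6-fold to 50 / 5 = 10-fold in the first four rows, and about 17 / 5 = 3.4-fold in the last.
- The share of false claims that arise with a non-significant primary test is 47 / 50 = 94% in the first row and 24 / 28 = 86% in the fourth.

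**Left out of the 19.** The Cochran-Mantel-Haenszel responder and partial-responder tests, the batch comparison on MADRS, and the repetition of efficacy analyses in the ITT and PP sets (SAP 6.1) would all add further tests.

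**The case against.** The best defence has four parts.

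1. **This is a proof of concept and the conclusion sits elsewhere.** SAP 6.1 ties the primary conclusion to the primary endpoint in the ITT population, and the protocol synopsis names only descriptive statistics as the method. This stands as mitigation: leaving secondary tests unadjusted would not by itself deserve comment. But none of this text withdraws the secondary claim rule, so both rules apply.
2. **The sentence may only set an order.** It can be read as saying that an omnibus result is not enough until a pairwise test supports it. That is a fair reading, and the working uses it. It limits error within one endpoint, not across 19.
3. **Correlation is probably high.** All visits share the Visit 2 baseline, LOCF repeats a dropout's last value, and several scales rate overlapping symptoms. This is a good reason to give more weight to the lower rows of the table. Even the last row is more than three times nominal for any claim.
4. **The harm is indirect.** No passage makes a dose or go/no-go decision depend on secondary p-values. This also stands. A misleading choice for the next phase is a risk that follows from how claims are used, not a step in the plan.

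A reader might infer that a false secondary claim is more likely than not. The documents do not support that. A figure clearly above one half needs near-independence or pairwise tests run without the Kruskal-Wallis step, and SAP 6.4.2 describes that step. Nor does the plan allow a secondary result to replace the primary conclusion.

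**Conclusion.** The gap is real but moderate. SAP 6.4.2 pre-specifies claims on 19 secondary comparisons at two-sided 0.05, and nothing controls error across them. With no drug effect, the chance of at least one false claim is about 28 to 50% over the main range of assumed correlations and about 17% at 0.9/0.9. A false claim favouring the drug, the kind most likely to mislead later planning, has a chance of about 15 to 28% over the main range. Most false claims occur when the primary test is not significant.

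These sizes rest on assumed correlations, normally distributed changes, exactly 20 patients per arm and complete data. The 62% is the independence figure for Kruskal-Wallis alone and should not be quoted as the expected error.

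**What to change.** Replace the claim sentence in SAP 6.4.2 with:

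*Secondary p-values are nominal and unadjusted for multiplicity; they are reported descriptively and no treatment effect will be claimed from them. Confirmatory claims are limited to the primary endpoint (Kruskal-Wallis, then Wilcoxon with Holm).*

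This agrees with SAP 6.1 and 6.6.5 and changes no test, estimate, sample size or primary analysis. The cost is that the sponsor gives up claims of significance on secondary endpoints; all estimates and p-values are still reported. It is a cheap improvement.

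If the sponsor wants to keep secondary claims, a pre-specified hierarchy or Holm across the family would also control the error. With Holm across 19 tests the first threshold is 0.05 / 19 = 0.0026, which is demanding at 20 patients per arm.

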**CONFIDENTIAL**

Project No. BLI-1005-002

Statistical Analysis Plan for PDC-1421

“Final” Page 23 of 34

Protocol Version: 2.3

SAP Version: 20180626\_01

second batch are “HDP-045A-070119” for PDC-1421 and “HDP-045C-070119” for placebo. Subjects with baseline visit later than 2018/02/13, or those who were enrolled before 2018/02/13 and got drugs after 2018/03/15 will be classified into the subgroup of the second batch.

The responder and partial responder is defined by the net change in total score of MADRS (responders are defined as participants with a  $\geq 50\%$  decrease in total score from baseline; partial responders are defined as participants with at least 25% and no more than 50% decrease in total score from baseline). The percentage difference between treatment groups will be examined by Cochran-Mantel-Haenszel test.

The same definitions of partial responder will be used for HAM-D-17. The difference between the treatment will be compared with Cochran-Mantel-Haenszel test as well.

All statistical tests used will be two-tailed with  $\alpha = 0.05$ .

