1.1.1 Preparation

Raw materials originated from *P. tenuifolia* were obtained from Shanxi, China. After having been cleaned, and residual stems removed, the root was sun-dried and become the botanical raw material for producing the study drug (PDC-1421 capsule). Raw materials shall comply with physical/chemical specifications, and fingerprint determination via HPLC and TLC shall show desired contents. The materials shall comply criteria for heavy metal, pesticide residues and aflatoxins to avoid contaminations. Acceptable raw materials were water extracted, partially purified by column chromatography, concentrated, and spray-dried to become the drug substance PDC-1421, a yellowish powder. The yield rate from raw materials to PDC-1421 is about 1.4 %. Formulation and encapsulation of drug substance PDC-1421 produced the final product of PDC-1421 Capsule. Specifications of PDC-1421 Capsule are tabulated in Table 1.

Table 1. Specifications of PDC-1421 Capsule

Test Items	Specifications
Physical Appearance	Yellowish Granules in brownish capsule.
Loss on Drying	NMT 6%
Water Extractives	NLT 80%
Dilute-Alcohol Extractives	NLT 70%
Total Ash	NMT 5%
Acid-Insoluble Ash	NMT 4%
Alcohol Extractives	NLT 38%

TLC	1. One grayish blue band has same R_f value as reference standard (3',6-disinapoysucrose); 2. One watchet blue band has same R_f value as reference standard (Glomeratose A).
HPLC of markers	1. $7.0 \text{ mg/g} \leq \text{Glomeratose A} \leq 17.5 \text{ mg/g}$. 2. $38 \text{ mg/g} \leq 3',6\text{-Disinapoysucrose} \leq 95 \text{ mg/g}$.
UV Spectrum	λ_{max} : 230 – 240 nm; 315 – 325 nm
IR Spectrum (cm⁻¹, %T)	Peak at: 3380 ± 100 Broad, 2938 ± 20 Sharp, 1605 ± 10 Sharp, 1455 ± 10 Sharp, 833 ± 10 Sharp.
pH	Dissolved in distill deionized water at a concentration of 0.1 g/ml, $3.8 \leq \text{pH} \leq 5.8$.
Uniformity	90-110%
Weight Variation	90-110%
Heavy Metal	Cu < 20 ppm, As < 1 ppm, Pb < 5 ppm, Cd < 0.2 ppm, Hg < 0.1 ppm
Microbial Purity	Total aerobic plate count: NMT 10^3 CFU/g Mold and yeast count: NMT 100 CFU/g Escherichia coli : Undetectable Staphylococcus aureus : Undetectable Salmonella : Undetectable

NMT: not more than; NLT: not less than

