5.2.3 Part II.- Treatment Period (Visit 2~5) and Follow-up (Visit 6)

Laboratory data and results of other tests and evaluation shall be obtained at screening to determine the appropriateness of subject enrolled in this study. Subjects who meet the eligibility criteria will be enrolled and take study drugs. Baseline data (Visit 2), including physical examination, vital sign, ECG, hematology, blood chemistry, HAM-D-17, CGI, HAM-A, MADRS, DSSS, C-SSRS and concomitant medication evaluation, will be collected before dosing study drug. At visits 2, 3 and 4 (weeks 0, 2 and 4), each subject will be dispensed a supply of study drug sufficient for 2-week treatment period. The subjects will be instructed to take one dose (i.e., two capsules) after a meal thrice daily for every week. Subjects will be assessed every two weeks and receive the study drug for next two weeks till the end of trial. At visits 2, 3, 4 and 5, the safety and efficacy parameters will be evaluated by the following items.

- Physical examination: skin, head, neck, eyes, ears, nose, throat, heart, lungs, abdomen (liver, spleen), neurological examination, lymph node and extremities.
- Vital sign: heart rate, blood pressure, body temperature
- ECG
- Hematology: RBC, WBC, platelets, hematocrit, hemoglobin, prothrombin time (PT), partial thromboplastin time (aPTT). If the interval of visit 1 and visit 2 is within 7 days, Hematology test of visit 2 can be skipped.
- Blood chemistry: AST, ALT, LDH, total bilirubin, BUN, serum creatinine, free thyroxine (FT4), TSH, sodium, calcium, potassium, LDL, HDL, triglyceride, cholesterol. If the interval of visit 1 and visit 2 is within 7 days, Blood chemistry test of visit 2 can be skipped.
- HAM-D-17, CGI, HAM-A, DSSS, MADRS, C-SSRS and concomitant medication evaluation.
- AE/SAE evaluation
- Drug accountability

Follow-up visit will be performed at visit 6 after one week of the last dose administration.

The test items are outlined in the following:

- Physical examination: skin, head, neck, eyes, ears, nose, throat, heart, lungs, abdomen (liver, spleen), neurological examination, lymph node and extremities.
- Vital sign: heart rate, blood pressure, body temperature
- ECG
- Hematology: RBC, WBC, platelets, hematocrit, hemoglobin, prothrombin time (PT), partial thromboplastin time (aPTT)
- Blood chemistry: AST, ALT, LDH, total bilirubin, BUN, serum creatinine, free thyroxine (FT4), TSH, sodium, calcium, potassium, LDL, HDL, triglyceride, cholesterol.

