11.3 Study Center File Management

It will be the responsibility of the clinical monitors/CRC to maintain the study center file. The study center file for this study will contain, but not limited to, the information listed below:

- (1) Investigator Brochure.
- (2) Signed Protocol and Amendments approved by both Regulatory Authority and IRB.
- (3) Copies of Regulatory Authority and IRB approval letter for this study.
- (4) Curricula Vitae of Investigator and sub-investigator.
- (5) Other documentation of IRB complied with regulations by Regulatory Authority.
- (6) Copy of Informed Consent Form approved by both Regulatory Authority and IRB.
- (7) All IRB correspondence (reports to IRB, including reports of all death and adverse experience, annual progress reports, final reports, acknowledgement of receipt of report and actions taken by IRB).
- (8) All IND Efficacy and Safety Reports sent to the Investigator.
- (9) Laboratory certification and/or license.
- (10) All written correspondence with the Sponsor.
- (11) Normal ranges of laboratory value for all laboratory tests required by Protocol.
- (12) CRA monitoring logs.
- (13) Drug Invoices and Drug Dispense/Return Records.

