### **6.6.8 Examination of Subgroups**

No subgroup analysis was conducted in the study. All center data will be pooled together for analyses of efficacy endpoint.

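### The SAP defines the two product batches by lot number but sorts subjects by calendar date, so batch exposure can be misclassified in the additional MADRS batch analysis

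*SAP*

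**What the plan says.** SAP section 6.4.2 states that "the effect of different product batches (or batch number)- the first batch and the second batch, on MADRS will also be examined". The product side is defined by lot: one PDC-1421 lot and its matching placebo lot "are classified into the first batch of product", and a second pair of lots makes up the second batch.

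The subject side is defined by date. The second-batch subgroup holds subjects whose baseline visit is later than 2018/02/13, and "those who were enrolled before 2018/02/13 and got drugs after 2018/03/15 will be classified into the subgroup of the second batch". No separate rule places subjects in the first batch, so everyone else presumably falls there. There is no category for a subject who took both lots. No test or contrast is named for the batch effect, either in section 6.4.2 or in the methods table in section 7.1.

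On supply, protocol section 5.2.3 says that at visits 2, 3 and 4 "each subject will be dispensed a supply of study drug sufficient for 2-week treatment period". The bag label in protocol section 3.5.4 has a lot number field. Protocol section 11.3 puts "Drug Invoices and Drug Dispense/Return Records" in the study center file.

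SAP section 6.6.8 says: "No subgroup analysis was conducted in the study".

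**The concern.** The analysis asks about a product property, the lot, but the grouping variable is a pair of calendar dates. The two agree only if every site changed lots in step with those dates, and neither document says when each lot reached a site. With three dispensings per subject, some subjects can take both lots, and the rule must then put them wholly in one group.

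The second clause is the clearest case. The first clause already takes every baseline after 2018/02/13. The second can add only subjects who began treatment earlier and so had already been supplied, and it calls them second batch without qualification.

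What is at stake is how a secondary, additional analysis can be read. PDC-1421 is a botanical extract, so a batch comparison is a reasonable thing to plan, but its result means little if the groups do not reflect what subjects took. SAP section 6.6.8 also denies any subgroup analysis, while section 6.4.2 forms a batch subgroup.

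**Working it through.** **Inputs**
- Dispensing at Visits 2, 3 and 4, that is days 0, 14 and 28 (protocol section 5.2.3).
- Visit window ±2 days (protocol Table 16; SAP section 5.2.3).
- Enrolment takes place at Visit 2 (protocol sections 4.3 and 5.2).
- Rule dates 2018/02/13 and 2018/03/15 (SAP section 6.4.2).

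**1. The plan's own supply figure.** 3 dispensings × 14 days × 3 packs per day = 126 packs. This matches protocol Table 14 and confirms three occasions on which the lot could change.

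**2. Whom the second clause can reach.** The latest enrolment before 2018/02/13 is 2018/02/12. The latest in-window Visit 4 is day 28 + 2 = 30, and 2018/02/12 + 30 days = 2018/03/14. That is not after 2018/03/15, so no in-window subject is caught. The first qualifying date, 2018/03/16, is day 32 for this subject, 2 days beyond the window, and later still for earlier enrolments. If enrolment were read as the screening visit, the result is the same: a Visit 2 on 2018/02/13 gives a last in-window dispensing on 2018/03/15, which is also not after that date.

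**3. What those subjects took.** All had the Visit 2 bag before 2018/02/13. For the Visit 3 bag also to fall after 2018/03/15, Visit 3 would have to be on day 32 or later instead of day 14 ± 2. Normally, then, two of three bags precede the second date. If only the Visit 4 bag is from the new lot, the second-lot share is 14/42 = 33% and the earlier share is 28/42 = 67%. With Visit 4 on day 32, the earlier share is 32/46 = 70%. The rule counts these subjects as 100% second batch.

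**4. The uncovered date.** A baseline on 2018/02/13 is neither later than that date nor before it, so neither clause applies.

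**5. Continuing subjects between the two dates.** The documents do not say which lot they received, so two cases must be shown.
- *They kept the first lot.* The two dates are 30 days apart, exactly the latest in-window Visit 4. The rule then separates the lots cleanly for in-window subjects.
- *The new lot went to everyone after 2018/02/13.* The earliest baseline with an in-window dispensing after that date is 2018/02/14 − 30 days = 2018/01/15. That subject could have one new bag, 14/42 = 33%. On the nominal schedule, baselines from 2018/01/31 to 2018/02/13 have two new bags (2018/01/31 + 14 days = 2018/02/14), 28/42 = 67%. None of these subjects is labelled second batch.

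**6. Illustrative size for the second clause.** Assume k caught subjects, each with 28/42 first-lot exposure, among n labelled second batch, a clean first-batch group, and an effect proportional to days on the lot. The batch difference is then multiplied by 1 − k × (28/42)/n.

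| n (assumed) | k = 1 | k = 3 | k = 6 |
|---|---|---|---|
| 20 | 0.97 | 0.90 | 0.80 |
| 30 | 0.98 | 0.93 | 0.87 |
| 40 | 0.98 | 0.95 | 0.90 |

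Neither k nor n is in the documents.

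**The case against.** The strongest reply is that the dates may be a good proxy. The 30-day gap equals the latest in-window last dispensing, which looks deliberate. The two SAP versions were approved in April and June 2019 (SAP section 11.4), more than a year after the dates, so the authors could have known the supply history. If continuing subjects finished on the first lot, in-window subjects are sorted correctly. This stands. A reader might infer that the groups are wrong; the documents show only that they can be.

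Three further inferences are tempting and also lack support.
- *Misclassification hides a batch effect, and the null result is then used to justify pooling.* Neither document gives the batch result that role; SAP section 6.6.8 pools centers, not batches. With no contrast named, the overall direction of any bias cannot be fixed. It also cannot be said that the SAP compares batches across all arms together.
- *Batch variation could invert the two doses.* The specification row "HPLC of markers" in protocol Table 1 allows each marker a 2.5-fold range (95/38 and 17.5/7.0), against a 2-fold dose difference. But the arms are defined by milligrams of extract, the released content of the two lots is not given, and nothing shows that marker content tracks effect. This would in any case be a point about batch variability, not classification.
- *Each misclassified subject is 5% of an arm.* The relevant denominator is the batch subgroup, whose size is not stated.

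It may also be said that actual exposure is not certain to be in the database. That is fair: the label field and the filed records show that lots should be traceable, not that the lot of each bag is a database variable.

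The reply leaves four things untouched: a lot-defined exposure is assigned by date; there is no mixed category; anyone caught by the second clause is labelled wholly second batch despite earlier supply; and sections 6.4.2 and 6.6.8 disagree.

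**Conclusion.** The point holds as a weakness in the classification rule. The rule can misclassify batch exposure in two ways. Subjects dispensed out of window after 2018/03/15 are counted wholly as second batch, with typically about two thirds of their treatment days on earlier supply; this share assumes that only the last bag was new and that the earlier bags were first lot. If the new lot was given to continuing subjects between the two dates, in-window subjects with baselines from about 2018/01/15 could have 14 to 28 of 42 days on it without the second-batch label. A baseline on 2018/02/13 is unassigned.

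The number of subjects affected is unknown and may be small, possibly none among those seen in window. The primary Kruskal-Wallis test with Holm-adjusted comparisons does not use the batch variable and is unaffected. The correction is still worth making, because the stated rule is a proxy for information that the dispensing records should hold directly.

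**What to change.** In SAP section 6.4.2, replace the date rule with the lot number recorded for each bag dispensed at Visits 2, 3 and 4. Classify each subject as first batch only, second batch only, or mixed. Report mixed subjects separately. Within each batch, summarise the PDC-1421 versus placebo difference in MADRS change descriptively. Amend section 6.6.8 to list this as the one exploratory subgroup.

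The cost is one derived variable and a short SAP amendment, plus retrieval of lot numbers from the dispense/return records if they are not in the database. The two pure-batch groups become slightly smaller. With 60 subjects over three arms and three categories, the average is 60/9 = 6.7 per cell, so the summary should remain descriptive.
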